5.2.1.1 Time Point Capping for AUC Endpoints Only

If the relative time (from time 0) of the last scheduled timepoint for the AUC is greater than or less than the nominal terminal time for the AUC endpoint being calculated, i.e. 24 hours for AUC_{0-24} , then the calculated AUC will be scaled by the ratio of actual time to nominal time. This will ensure that the time considered for AUC will be consistent for each subject.

For example, if time 0 is at 8:00 am and the 24 hour time point is 7:50 am the next day, then the AUC will be multiplied by 1440/1430 ([nominal minutes]/[actual minutes]).

5.2.2 Time to First Rescue Medication Use

The time to first rescue medication use will be derived relative to Time 0, Day 1. The units of hours will be used for time to event analysis.

5.2.3 Amount of Rescue Medication

The average of the total amount of ibuprofen taken (400 mg per tablet), total amount of acetaminophen (325mg per tablet) and hydrocodone taken (5 mg per tablet), or instances of any rescue medication (mg) taken during 0-24, 24-48, 48-72,0-48, and 0-72 hours by treatment group will be derived. Missing amount of rescue medication data will not be imputed. Summarize out of clinic rescue tablets/usage/add mgs.

In addition, the total amount of opioids in morphine milligram equivalents (MME) taken during the time periods will be summarized by treatment group. Both in clinic and out of clinic (Diary). In clinic, subjects should only receive hydrocodone and a 1:1 conversion of hydrocodone to MME will be utilized; should subjects take any other opioid, then the CDC conversion guide will be used for converting to MME:

https://www.cdc.gov/drugoverdose/pdf/calculating_total_daily_dose-a.pdf

5.2.4 Proportion of Subject Who Did Not Use Rescue Medication

The proportion of subjects who did not use rescue medication through 24, 48, and 72 hours will be derived as the number of subjects who did not use any kind of rescue medication through 24, 48 and 72 hours divided by the number of subjects per treatment group that were still in the trial through that time point.

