 - Multiple imputation will be used to impute values at the scheduled assessment times for subjects that discontinue. For the purposes of imputation, unscheduled values and pre-rescue values will not be included, but will be added back into the dataset prior to calculating the AUC; however, scheduled values will be replaced with pre-rescue values during the censoring period prior to the imputation (and solely for the purpose of imputation). First, subjects that discontinue for reasons other than lack of efficacy (LOE) and

adverse events (AEs) will have their values imputed within treatment group with MI assuming MAR with covariates for all observed time points. For subjects who discontinue due to AEs or LOE, the MI will be based off the distribution of worst values through the time of discontinuation. This will be done iteratively for each time point starting at the earliest time point with missing data; covariates will be included for observed data through that time point. Full details of the MI algorithm are given in [Appendix 21.2](#).

In general, the area under the curve (AUC) from start time of interest, t_{start} , to end time of interest, t_k , for each subject will be calculated using the linear trapezoidal method. All pain assessments (including unscheduled) will be used in the calculation.

$$AUC_{t_{start}-t_k} = \sum_{i=start}^{k-1} \frac{1}{2} * (Pain_i + Pain_{i+1}) * (t_{i+1} - t_i)$$

Where i indexes the timepoints from 0 hour to 72 hours as 0 to 24; $start$ is the index value of the starting time; k is the index value of the end time; t_{start} is the start time of the AUC to be calculated; t_k is the end time of the AUC to be calculated; $Pain_i$ is the NRS pain intensity score at index i ; t_i is the time at index i . **Note:** The index count will be adjusted on an individual basis to account for unscheduled assessments and pre-rescue assessments. Calculations will be performed at a 1-minute precision, but final values will be scaled to hours, thus the AUC_{0-24} will be scaled 0-240.

For the primary efficacy endpoint the formula would be as follows:

$$AUC_{0-24} = \sum_{i=0}^{16-1} \frac{1}{2} * (Pain_i + Pain_{i+1}) * (t_{i+1} - t_i)$$

Note: The index count will be adjusted to account for unscheduled assessments.

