5.2.7 Proportion of Subjects Who Are Opioid Free

The proportion of subjects who are opioid free 0-<24, 0-<48 and 0-<72 hours and 24-<48 hours and 48-72 hours will be derived as the number of subject who did not take opioids divided by the number of subjects per treatment group. Likewise, the proportion of subjects that are opioid free starting at 0, 12, 24, 36 hours will be reported. Subjects that drop out of the study prior to a given time point will be assumed to have not subsequently taken opioids, unless concomitant medication or diary data suggest that an opioid was available to them at that time (whether or not the subject reported taking it in the period in question).

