12.3 Multiple Comparisons / Multiplicity

A fixed sequence method at alpha=0.05 for the primary and key secondary efficacy endpoints will be used to control for multiplicity. The following will be the sequence for testing:

1. 400 mg Q6H compared to placebo on mean AUC_{0-24} of NRS of pain intensity scores
2. 1600 mg QD compared to placebo on mean AUC_{0-24} of NRS of pain intensity scores
3. 400 mg Q6H compared to placebo on time to first rescue medication use after time 0
4. 400 mg Q6H compared to placebo on proportion of subjects who were opioid free through 24 hours
5. 1600 mg QD compared to placebo on time to first rescue medication use after time 0
6. 1600 mg QD compared to placebo on proportion of subjects who were opioid free through 24 hours
7. 400 mg Q6H compared to placebo on proportion of subjects who were opioid free through 48 hours

8. 1600 mg QD compared to placebo on proportion of subjects who were opioid free through 48 hours
9. 400 mg Q6H compared to placebo on proportion of subjects who were opioid free through 72 hours
10. 1600 mg QD compared to placebo on proportion of subjects who were opioid free through 72 hours

The testing procedure will stop once a p-value in the sequence is greater than 0.05. P-values that are less than or equal to 0.05 prior to stopping, will be declared statistically significant; p-values after stopping will be nominal. P-values obtained from the stratified log-rank test stratified by site will be used to for the endpoints that compare the time to first rescue medication use after time 0 by treatment group.

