13.2 Key Secondary Efficacy Endpoints

Analysis of the key secondary efficacy endpoints will be performed using the Full Analysis Set.

Time to first rescue medication use after time 0 (hours)

A stratified log-rank test stratified by site will be used to compare the time to first rescue medication use after time 0 by treatment group. The follow-up time will end at 72 hours. The time at which subjects discontinue due to the lack of efficacy will be considered as an event. Subjects who do not take rescue medication and who do not discontinue for lack of efficacy will be censored at 72 hours or their last follow-up time, whichever is earlier. The estimate and 95% CI's for the median time to event will be summarized by treatment group, where

event is the time to first rescue medication use after time 0. The p-value of the stratified test of equality over treatment group for each pairwise comparison will be summarized.

Sample SAS code:

```
proc lifetest data=indata;
  time time*cnsr(1);
  strata site /group=trt;
run;
```

where time is the time to first rescue or censor, cnsr is the censor status, site is the site variable, and trt is the treatment group variable.

In addition, a stratified by site Cox proportional hazards model treatment group as a factor will be used to analyze the time to rescue medication or censoring. The follow-up time will end at 72 hours. The time at which subjects discontinue due to the lack of efficacy will be considered as an event. Subjects who do not take rescue medication and who do not discontinue for lack of efficacy will be censored at 72 hours or their last follow-up time, whichever is earlier.

The hazard ratio and 95% confidence interval will be summarized for each pairwise comparison as defined previously.

Kaplan-Meier curves of time to first rescue will be presented.

Sample SAS code:

```
proc phreg data=indata covsandwich;
  class trt(ref="Placebo");
  model time*cnsr(1)= trt/ ties=exact;
  strata site;
run;
```

In addition, the number and percentage of subjects taking rescue medication or discontinuing due to lack of efficacy and the number and percentage of subjects censored will be summarized.

Proportion of subjects who were opioid free through 24, 48, and 72 hours

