13.3 Secondary Efficacy Endpoints

Analyses of the secondary efficacy endpoints will be performed using the Full Analysis Set.

The following secondary efficacy endpoints will be analyzed similarly as the primary analysis for the primary efficacy endpoint.

- The mean AUC₀₋₄₈ of NRS of pain intensity scores

- The mean AUC_{0-72} of NRS of pain intensity scores
- The mean AUC_{0-4} of NRS of pain intensity scores
- The mean AUC_{0-6} of NRS of pain intensity scores
- The mean AUC_{0-12} of NRS of pain intensity scores
- The mean AUC_{24-48} of NRS of pain intensity scores
- The mean AUC_{48-72} of NRS of pain intensity scores

Amount of rescue medication taken during 0-24, 24-48, 48-72, 0-48, and 0-72 hours

The following will be summarized:

- The number of tablets of ibuprofen taken during 0-24, 24-48, 48-72, 0-48, and 0-72 hours.
- The number of tablets acetaminophen-hydrocodone taken during 0-24, 24-48, 48-72, 0-48, and 0-72 hours.
- The number of instances of any rescue medication taken during 0-24, 24-48, 48-72, 0-48, and 0-72 hours.
- The amount of opioids in Morphine Milligram Equivalents (MME) taken during 0-24, 24-48, 48-72, 0-48, and 0-72 hours

Each of the above items will be analyzed using ANOVA with treatment group and site as factors in the model by rescue medication type.

The LS mean (SE), 95% confidence intervals, and p-values will be presented by treatment group. The LS mean difference (SE), associated 95% confidence intervals, p-values, and Cohen's d will be presented by treatment group pairwise.

Proportion of subjects who did not use rescue medication through 24, 48, and 72 hours

Given the in-clinic setting of this study, subjects with no records of rescue medication dispensation will be assumed to not have used any rescue medication.

The proportion of subjects who did not use rescue medication (neither acetaminophen-hydrocodone oral tablets nor ibuprofen nor any other) through 24, 48, and 72 hours will be summarized and will be analyzed using a stratified Cochran-Mantel-Haenszel (CMH) test controlling for site.

The risk difference, 95% confidence interval and p-values will be provided by treatment group pairwise.

Proportion of subjects who were opioid free during 24-48 hours and 48-72 hours

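### SAP 5.2.4 removes known rescue users who leave early from the no-rescue denominator, in conflict with the Full Analysis Set named in SAP 13.3

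*SAP*

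**What the plan says.** The no-rescue proportion through 24, 48 and 72 hours is a secondary endpoint (SAP 12.1). Two sections define it.

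- **SAP 5.2.4 (derivation).** The count of subjects with no rescue of any kind is "divided by the number of subjects per treatment group that were still in the trial through that time point".
- **SAP 13.3 (analysis).** "Analyses of the secondary efficacy endpoints will be performed using the Full Analysis Set". The test is a CMH test controlling for site. With reference to the in-clinic setting, the section adds that "subjects with no records of rescue medication dispensation will be assumed to not have used any rescue medication".

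The FAS in SAP 4 requires randomization, a postoperative dose and the bunionectomy. The FAS in Protocol 9.4 requires randomization, a dose, the surgery and one postoperative pain score. Neither requires remaining in the trial to a given hour, and both documents assign all efficacy endpoints to it. SAP 19 declares no change from the protocol analyses.

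Two related endpoints treat leavers differently:

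- **Opioid-free (SAP 5.2.7)** is "the number of subject who did not take opioids divided by the number of subjects per treatment group". Leavers "will be assumed to have not subsequently taken opioids, unless concomitant medication or diary data suggest that an opioid was available to them".
- **Time to first rescue (SAP 13.2):** "The time at which subjects discontinue due to the lack of efficacy will be considered as an event".

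**The concern.** A no-rescue outcome through 24 hours is settled as soon as rescue is taken. If that subject then leaves, nothing about the outcome is missing. A denominator limited to those who stay nevertheless deletes the failure and raises the arm's percentage.

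The two sections also describe different sets of subjects. A CMH test on the FAS needs a yes or no for every FAS subject, and 5.2.4 supplies none for anyone who left. Two programmers could therefore report different percentages from the same data, or a percentage and a test that rest on different subjects.

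**Working it through.** **Inputs.** The plan states no expected no-rescue percentage, opioid-free percentage or dropout rate, so there is no figure of its own to reproduce for this endpoint. The only input taken from it is the group size, which does reproduce. SAP 3.5 assumes a difference of 23, SD 50, two-sided 0.05 and about 80% power. The normal formula gives 2 × (1.960 + 0.842)² × (50/23)² = 74.2, so 75 per arm. The t-test gives 75.2, so 76 per arm, with power 0.804. Then 76/0.95 = 80 per arm. The 5% is an allowance for exclusion from the primary analysis, not a dropout rate for this endpoint. All counts below are assumptions.

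**Step 1: one arm.** Let x of 80 be rescue-free and let k known rescue users leave before the time point. The FAS proportion is x/80. The 5.2.4 proportion is x/(80 − k).

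| x | FAS | k = 2 | k = 4 | k = 8 |
|---|---|---|---|---|
| 8 | 10.0% | 8/78 = 10.3% | 8/76 = 10.5% | 8/72 = 11.1% |
| 16 | 20.0% | 16/78 = 20.5% | 16/76 = 21.1% | 16/72 = 22.2% |
| 40 | 50.0% | 40/78 = 51.3% | 40/76 = 52.6% | 40/72 = 55.6% |

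For known users the shift within an arm is always upward.

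**Step 2: two arms.** Take 16/80 in both. If 8 known users leave active and 2 leave placebo, the difference is 16/72 − 16/78 = 22.2% − 20.5% = +1.7 points where the FAS gives 0. Swap the losses and it is −1.7. Equal losses leave a zero difference at zero.

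**Step 3: leavers with no rescue record.** Take 80 subjects, of whom 8 leave: 4 after recorded rescue and 4 with no record. Of the 72 who stay, 16 are rescue-free.

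- 5.2.4, leavers out of numerator and denominator: 16/72 = 22.2%.
- FAS, no-record leavers counted rescue-free: 20/80 = 25.0%.
- FAS, no-record leavers counted as failures: 16/80 = 20.0%.

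The FAS denominator settles the 4 known users. The other 4 still need a stated rule, worth 4/80 = 5.0 points here.

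**Step 4: the opioid-free rule in 5.2.7.** Suppose a fraction p of an arm would stay opioid-free to the time point and a fraction q is still opioid-free when subjects leave. Suppose also that a fraction d of the arm leaves while opioid-free, with no sign that an opioid was available. The rule then reports p + d(1 − p/q). With p = 0.30 and q = 0.50 in both arms:

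- d = 10% active, 2.5% placebo: 0.075 × (1 − 0.6) = +3.0 points.
- d = 5% v 2.5%: 0.025 × 0.4 = +1.0 point.
- d = 2.5% v 10%: −3.0 points.
- d = 10% v 2.5%, half of these leavers caught by the availability exception: 0.075 × (0.5 − 0.6) = −0.75 points.
- d equal in both arms: 0.

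Sign and size both turn on rates that the documents do not give.

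**The case against.** **Naming the FAS does not by itself forbid an evaluable denominator.** SAP 5.2.5 divides the pain-free count by subjects with non-missing NRS, also for a secondary endpoint on the FAS. This stands for leavers whose outcome is unknown. It does not help with a leaver whose rescue use is on record, because that outcome is known.

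**A reader might infer that 13.3 contains an opposing dropout rule.** The no-record sentence would then score every leaver without a record as rescue-free. The text does not go that far: it is a convention for absent dispensation records in clinic and does not mention dropout. The firm conflict is between the FAS and the denominator in 5.2.4. Likewise, placing no-record leavers in the numerator but not the denominator is a strained reading, and nothing here rests on it.

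**A reader might infer an inflated type I error.** The no-rescue proportion is not among the ten tests in SAP 12.3, so its p-value supports no controlled claim.

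**A reader might infer that 5.2.7 is also wrong.** Its opioid-free tests are numbers 4 and 6 to 10 of the fixed sequence, and its handling of lack-of-efficacy dropouts differs from 13.2 and from the worst-value imputation in 5.2.1. That is different handling across different endpoints, not a contradiction: leaving for lack of efficacy is not taking an opioid. Opioids recorded before departure still count, and apparent availability alone defeats opioid-free status. The plan also seeks data after discontinuation: completion of end-of-treatment and follow-up assessments (Protocol 4.5.2), rescue recording to the clinic follow-up visit (Table S-1 footnotes), and all medications to the telephone call (Protocol 4.7). The rule therefore bites mainly where such data are absent, for example after full withdrawal of consent.

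What remains is that the planned sensitivity analyses (SAP 13.1.2) cover only the primary endpoint. More for a key secondary endpoint in a proof-of-concept study would be useful, but their absence is not an error.

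**Conclusion.** The denominator in SAP 5.2.4 is wrong for subjects with recorded rescue use who leave early, and it does not agree with SAP 13.3, Protocol 9.4 or the sister endpoint in SAP 5.2.7. In the 20.0% example the overstatement is 0.5 to 2.2 points for 2 to 8 such leavers out of 80. It grows with the true percentage and with the number who leave. The between-arm bias can run either way.

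Confidence in the defect is high, because it rests on the text. Confidence in its size is low, because every count is assumed and dropout over 72 inpatient hours may be small. The primary analysis and the fixed sequence are untouched. The opioid-free dropout rule is a matter for an optional supportive analysis, not a finding of error.

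**What to change.** **SAP 5.2.4.** Use all FAS subjects in the treatment group as the denominator. Count any recorded rescue use from time 0 to the time point as failure, including use before dropout.

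**Leavers with no rescue record.** State one rule and use it in both 5.2.4 and 13.3. The no-record convention in 13.3 (rescue-free) is the closest existing text. It is an assumption, and it differs from 13.2: a subject who leaves for lack of efficacy without rescue would be an event there and a success here. Report the number of such subjects by arm and reason, so that the weight of the assumption is visible.

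**Cost.** SAP wording, one small table and slightly changed percentages, best settled before unblinding.

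**Optional.** For the opioid-free tests (numbers 4 and 6 to 10), keep the 5.2.7 rule as the main analysis. Add one supportive analysis that counts lack-of-efficacy dropouts before the time point as not opioid-free. Give the number of dropouts scored opioid-free by arm and reason. This analysis tends to favour the arm that loses fewer such subjects, so it should not replace the main rule.

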5.2.5 Proportion of Subjects Who Are Pain Free (NRS ≤ 2)

The proportion of subjects who are pain free at each scheduled time point will be derived as the number of subject who have a NRS pain intensity score ≤ 2 divided by the number of subjects per treatment group with non-missing NRS values. If a subject took rescue medication within 4 hours prior to the timepoint, the subject will not be considered as pain free even if the NRS pain intensity score is ≤ 2 .

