4 ANALYSIS SETS

Randomized Analysis Set

The Randomized Analysis Set includes all randomized subjects. Subjects will be analyzed based on their randomized treatment assignment.

Safety Analysis Set

The Safety Analysis Set includes all randomized subjects who received at least one dose of study drug (ACP-044 or placebo). Subjects will be analyzed based on the treatment that they actually received. The Safety Analysis Set will be used for all safety analyses.

Full Analysis Set

The Full Analysis Set includes all randomized subjects who received at least one dose of study drug post operation and who have undergone bunionectomy. Subjects will be analyzed based on their randomized treatment assignment. The Full Analysis Set will be used for the analysis of all efficacy endpoints.

Per-protocol Analysis Set

The Per-protocol (PP) Analysis Set includes all subjects in the Full Analysis Set who did not have any protocol deviations that could potentially have a substantial impact on the primary efficacy outcome. The precise reasons for excluding subjects from the PP Analysis Set will be fully defined and documented in a separate PD log file prior to the clinical database lock. Subjects will be analyzed based on their randomized treatment assignment. The PP Analysis Set will be used for supportive analyses of the primary efficacy endpoint.

Pharmacokinetics Analysis Set

The Pharmacokinetics Analysis Set includes all subjects with at least one measurable ACP-044 plasma concentration.

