5.2.6 Number of Hours Subjects are Pain Free (NRS ≤ 2)

The number of hours subjects are pain free (from 0-72 hours) will be derived as follows:

A horizontal line will be drawn at NRS of 2 on a line plot of a subject's NRS pain intensity scores. Then the time between the hours of 0 and 72, inclusive, where NRS pain intensity score is less or equal to 2 will be summed; linear interpolation will be used to calculate the amount of time for when the line plot and horizontal line intersects. If a subject took rescue medication, the next 4 hours after taking any rescue medication will not be considered pain

free even if the NRS pain intensity score is ≤ 2 . Subjects that drop out will not have the time after they drop out considered to be ≤ 2 following their last reported NRS.

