The proportion of subjects who are opioid free (did not take acetaminophen-hydrocodone oral tablet as rescue medication or any other opioid) through 24, 48, and 72 hours and during 0-<24 hours, 24-<48 hours, and 48-72 hours will be analyzed using a stratified CMH test controlling for site.

The risk difference, 95% confidence interval and p-values will be provided by treatment group pairwise.

Proportion of subjects who are pain free (NRS <2) at 24, 48, and 72 hours

The proportion of subjects who are pain free at 24, 48, and 72 hours will be analyzed using a stratified CMH test controlling for site.

The risk difference, 95% confidence interval and p-values will be provided by treatment group pairwise.

Number of hours subjects are pain free (NRS <2)

The number of hours subjects are pain free will be analyzed using ANOVA with treatment group and site as factors in the model. Each active dose group will be compared to placebo using this model.

The LS mean (SE), 95% confidence intervals, and p-values will be presented by treatment group. The LS mean difference (SE), associated 95% confidence intervals, p-values, and Cohen's d will be presented by treatment group pairwise.

Global evaluation of study drug just before time of first rescue and at the end of 24, 48, and 72 hours

The global evaluation of study drug (GESD) will be summarized as a categorical and as a continuous variable for each visit and for each censoring approach:

- With all values reported as recorded
- With values following rescue censored
- With the pre-rescue values grouped with the subsequent time point and values following rescue censored

The GESD will be analyzed by visit using ANOVA with treatment group and site as factors in the model.

The LS mean (SE), 95% confidence intervals, and p-values will be presented by treatment group. The LS mean difference (SE), associated 95% confidence intervals, p-values, and Cohen's d will be presented by treatment group pairwise.

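### The pain-free proportion is computed only among subjects with an observed NRS score, so subjects who discontinue for lack of efficacy or an adverse event leave the comparison instead of counting as not pain free

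*SAP*

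**What the plan says.** SAP 5.2.5 takes the number of subjects with NRS at or below 2 at the time point, "divided by the number of subjects per treatment group with non-missing NRS values". The only rule there that turns a low score into a failure concerns rescue: "If a subject took rescue medication within 4 hours prior to the timepoint, the subject will not be considered as pain free". Nothing is said about discontinuation.

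SAP 13.3 sets the population, "Analyses of the secondary efficacy endpoints will be performed using the Full Analysis Set", and the test: the proportion "pain free at 24, 48, and 72 hours will be analyzed using a stratified CMH test controlling for site". It adds no missing-data rule for this endpoint, and neither does Protocol 9.5.4.

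Other parts of the SAP do say what happens to subjects who leave:

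- SAP 5.2.6 (hours pain free): "Subjects that drop out will not have the time after they drop out considered to be" at or below 2.
- SAP 13.2 (time to first rescue): discontinuation for lack of efficacy is an event.
- SAP 13.1.1 (primary estimand): dropouts for lack of efficacy or an adverse event get the distribution of worst observed pain. Other dropouts follow the distribution of their own arm.
- SAP 5.2.7 (opioid free): "the number of subject who did not take opioids divided by the number of subjects per treatment group", so everyone stays in the denominator, although most dropouts are then assumed to have taken no opioid.
- SAP 5.2.4 (no rescue): "divided by the number of subjects per treatment group that were still in the trial through that time point", which again drops those who left.

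**The concern.** Followed as written, SAP 5.2.5 is an observed-case analysis. A subject whose pain leads to withdrawal at 20 hours is not counted as a failure at 24, 48 or 72 hours; that subject is simply absent. A subject with the same pain who stays and takes rescue within 4 hours of the time point is a failure. The worse course has the milder effect on the arm's rate.

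The CMH test then compares those who remained, and the remaining group can differ between arms for reasons related to treatment. The risk difference, confidence interval and p-value promised in SAP 13.3 carry that selection. The planned sensitivity analyses for missing data (SAP 13.1.2.2) cover only the primary endpoint, so nothing in the plan would show how much the result depends on this rule.

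**Working it through.** **1. The plan's own figure.** SAP 3.5 gives a difference of 23, SD 50, 76 per arm, two-sided 0.05 and about 80% power. The normal approximation gives 80.9% and the noncentral t with 150 df gives 80.4%, so the figure reproduces. Also 76/0.95 = 80 per arm. This calculation concerns AUC over 0-24 hours. The documents state no expected rate, power or dropout for the pain-free proportion. The 5% in SAP 3.5 is an allowance for exclusion from the primary analysis, not a rate of missing NRS; it is the only loss figure available.

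**2. Formula.** Let p be an arm's pain-free rate with everyone in the denominator, and d the share with no score. If no dropout is pain free, the SAP 5.2.5 rate is p/(1-d) and the inflation is p·d/(1-d). More generally, if a share q of dropouts would have been pain free and the observed rate is p_obs, the bias is d·(p_obs - q). It vanishes when q = p_obs and is largest when q = 0.

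**3. One arm, 80 subjects (p is assumed, q = 0).** For p between 20% and 50%:

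| Share missing | Inflation of the arm's rate |
|---|---|
| 5% (4 of 80) | 1.1 to 2.6 points |
| 10% (8 of 80) | 2.2 to 5.6 points |
| 15% (12 of 80) | 3.5 to 8.8 points |

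**4. Treatment difference.** Assumed: 16/80 = 20% on placebo and 24/80 = 30% on active, a 10.0-point difference, with q = 0.

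| Dropouts, placebo / active | Placebo | Active | Difference |
|---|---|---|---|
| 4 / 0 | 16/76 = 21.1% | 24/80 = 30.0% | 8.9 |
| 0 / 4 | 16/80 = 20.0% | 24/76 = 31.6% | 11.6 |
| 4 / 4 | 16/76 = 21.1% | 24/76 = 31.6% | 10.5 |
| 10 / 2 | 16/70 = 22.9% | 24/78 = 30.8% | 7.9 |
| 2 / 8 | 16/78 = 20.5% | 24/72 = 33.3% | 12.8 |

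The last two rows use losses of 10% to 12.5% in one arm, above the 5% allowance. They are illustrations, not expectations.

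**5. Effect on the test.** Equal true rates of 20% to 50%, 80 per arm, q = 0, normal approximation to the two-proportion test without site strata. With 5% loss on active and none on placebo, the chance of a significant result favouring active is 3.6% to 5.1% instead of 2.5%. With 10% and none it is 5.2% to 10.1%. With 5% in both arms it stays at 2.5%.

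**The case against.** The best defence is that SAP 5.2.1 says missing NRS scores are multiply imputed and SAP 21.2 completes the series to 72 hours, so no score is missing when SAP 5.2.5 is applied. The text does not carry that far. SAP 21.2 names AUC records as the product of the imputation, and neither SAP 5.2.5 nor SAP 13.3 mentions imputed scores or pooling of CMH results. A denominator limited to non-missing scores would also have little purpose if all scores were filled. If imputation was intended, the SAP should say so.

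Second, the study is inpatient and two-step rescue is available, so most subjects in pain can take rescue without leaving and are then failures under the 4-hour rule. This stands: the bias needs discontinuation, imbalance between arms, and dropouts who are mostly not pain free. Dropout may well be low.

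Third, not every dropout is a failure. Protocol 4.5 lists reasons such as withdrawal of consent and investigator decision, and a subject leaving for an adverse event need not be in pain. This also stands, and the fix below separates the reasons. A pain-driven exit might, however, be recorded as use of a prohibited medication (Protocol 4.5 and 4.8), so recorded reasons will not sort subjects perfectly.

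Fourth, a reader might infer that SAP 5.2.6 scores the same subject as a failure, or that the Full Analysis Set is not really used. Neither goes that far. SAP 5.2.6 accumulates hours, and a dropout keeps the pain-free hours already earned. An available-case analysis within the Full Analysis Set is a recognised choice, though a weaker one here.

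**Conclusion.** The concern holds for this endpoint. SAP 5.2.5 removes dropouts for lack of efficacy or an adverse event from the comparison, out of line with SAP 5.2.6, SAP 13.2 and the primary estimand. At a 5% loss the inflation of an arm's rate is about 1 to 3 points. In the 20% and 30% example, a 5% loss in one arm shifts the 10-point difference to 8.9 or 11.6. All sizes rest on assumed pain-free and dropout rates and on dropouts not being pain free; if some would have been, the bias is smaller.

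Two stronger readings are not supported. One is that the rule favours ACP-044. The direction depends on which arm loses more such subjects: heavier loss on placebo hides benefit, heavier loss on active creates it. The other is that the trial's main conclusions are at risk. The endpoint is not among the ten tests in SAP 12.3, and the primary AUC has its own imputation and sensitivity analyses. This is a worthwhile repair to an ordinary secondary endpoint.

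**What to change.** Amend SAP 5.2.5 before unblinding:

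1. Use all Full Analysis Set subjects in the arm as the denominator.
2. Count scheduled times after discontinuation for an adverse event or lack of efficacy as not pain free.
3. For other discontinuations, choose one rule and state it. Either use the within-arm missing-at-random scores from SAP 5.2.1 and 21.2, with CMH results pooled over the imputations, or count the times as not pain free, in line with SAP 5.2.6. The second is simpler and does not depend on how the reason was coded. The first also needs a statement of how imputed scores, which the sample code does not round, are compared with the cut of 2.
4. Interpolate an intermittent gap only where observed scores lie on both sides. The AUC rule covers nothing else, and 72 hours is the last scheduled AUC time point. Count any remaining missing score as not pain free.
5. Keep the observed-case version as a sensitivity analysis.

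The still-in-trial denominator in SAP 5.2.4 should be reviewed at the same time. The cost is a few sentences of SAP text and one extra table, with no new data. The downside is that some dropouts who might have been pain free are counted as failures; comparison with the observed-case version will show how much that matters.
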